- After completion of surgery, the residual neuromuscular block will be reversed with injection of neostigmine 0.05 mg/kg and atropine 0.01 mg/kg. When patients become suitable for extubation, with stable hemodynamic and adequate muscle power, thorough oral and endotracheal suction followed by extubation will be done.
- Patients will be nursed in post anaesthesia care unit for monitoring of post operative vital signs and for post operative pain assessment by numeric pain scale score at 0-hour and management accordingly.
- Patients postoperative pain will be followed up at the ward at time interval 0, 1, 2, 4, 6 hours.
- Patients will undergo close monitoring for the first 6 hours after caudal injection for overdose or adverse reactions.
- The following factors will be assessed:
 - (1) Intra operative heart rate and blood pressure.
 - (2) Post operative pain assessment according to numeric pain scale score 1-10 as (0= no pain, 10 =worst imaginable pain) and hemodynamic parameters at 0, 1, 2, 4, 6 hours.
 - (3) Time to rescue analgesia (intravenous analgesia administered after

surgery) when the numeric pain scale score is 3 or higher. Patients with numeric pain scale score ≥ 3 at any point of time, will receive intravenous morphine 5mg.

- (4) Estimated blood loss and surgeon satisfaction of surgical field.
- (5) Total intra operative and post operative analgesia in both groups.
- (6) Common complications of caudal block in the postoperative period which include hypotension, bradycardia, lower limb numbness and urinary retention. These complications will be recorded and managed accordingly.

Measured outcomes:

Primary outcome:

- Determining the total amount of fentanyl that will be consumed as intra operative analgesia.

Secondary outcome:

- Determining the total amount of morphine that will be given as analgesia for the first 6 hours post operative.
- Analyzing the numeric pain scale score for the first 6 hours post operative.
- Detecting effect of continuous caudal epidural analgesia on intra operative and post operative hemodynamic changes.
- Identifying the time to the first demand for rescue analgesia.
- Justifying the use of continuous caudal epidural for analgesia in lumbar fixation surgeries.

Statistical analysis:

- Statistical analysis will be carried out using the statistical software SPSS program. Description of quantitative data as mean and standard deviation and qualitative data as number and percentage.

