- Comparison between the two groups will be done by using the Chi-square test, independent t-test or Mann-Whitney U-test according to the distribution of data. A p-value less than 0.05 will be considered statistically significant.

End point:

- Severe hemodynamic instability due to any surgical complication.
- Any surgical emergency that will need to reopen the patient in operating room.

- 6 hours post operative.

REFERENCES

- **Abdel Hady Sarah Mahmoud Farid Mahmoud, Ahmed Azza Youssef Ibrahim, Neamat-Allah Hatem Saaed Abdel Hamid, et al. (2022):** Combined caudal epidural with general anesthesia for lumbar discectomy. Ain Shams medical journal. 73(3): 695-704.
- **Benyahia Najoua Mokraï, Verster Ann, Saldien Vera, et al. (2015):** Regional anaesthesia and postoperative analgesia techniques for spine surgery – a review. Romanian Journal of Anaesthesia and Intensive Care. 22(1): 25-33.
- **El-Feky EM and Abd El Aziz AA. (2015):** Fentanyl, dexmedetomidine, dexamethasone as adjuvant to local anesthetics in caudal analgesia in pediatrics. Egypt J Anaesth. 31:175-80.
- **Eochagain Aisling Ni', Singleton Barry N., Moorthy Aneurin, Buggy Donal J. (2022):** Regional and neuraxial anaesthesia techniques for spinal surgery: a scoping review. British Journal of Anaesthesia. 129 (4): 598-611.

- **Hurley WR. (2010):** Acute postoperative pain. In: Miller RD, Eriksson LI, Fleisher LA, Wiener-Kronish JP, Young WL, editors. *Miller's Anesthesia*. 7th ed. Philadelphia: Churchill Livingstone. 2757-81.
- **Kao Sheng-Chin, Lin Chia-Shiang (2017):** Caudal Epidural Block: An Updated Review of Anatomy and Techniques. *BioMed Research International* 1:1-5.

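### Time to first rescue analgesia is censored at 6 h or earlier exit, so the stated mean, SD and t-test do not fit it; a censoring-aware summary and one matching test would

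*Protocol*

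**What the plan says.** Under Measured outcomes, the protocol names this secondary outcome: "Identifying the time to the first demand for rescue analgesia". Under Post-operative setting, rescue is triggered by a numeric pain score of 3 or more, and the scoring schedule is: "Patients postoperative pain will be followed up at the ward at time interval 0, 1, 2, 4, 6 hours".

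Under End point, three events close a patient's participation: "6 hours post operative", "Severe hemodynamic instability due to any surgical complication" and "Any surgical emergency that will need to reopen the patient in operating room".

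The Statistical analysis section gives one general rule. For summaries: "Description of quantitative data as mean and standard deviation and qualitative data as number and percentage". For tests: "Comparison between the two groups will be done by using the Chi-square test, independent t-test or Mann-Whitney U-test according to the distribution of data". It makes no exception for time to rescue and does not say what is recorded for a patient who never needs rescue.

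**The concern.** A patient who reaches 6 h without rescue contributes only the information that the time exceeds 6 h. One who leaves earlier contributes even less. This is right-censoring, and it follows from the design. Choosing the test by the distribution of the data does not address it, because the difficulty is a missing value rather than a skewed one.

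A mean, an SD and a t-test need a number for every patient. The two obvious ways to supply or avoid one lead to different results:

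- **Enter 6 h.** The mean becomes a mean restricted to 6 h, and should be labelled so. If rescue follows the scheduled scores, unrescued patients are also tied with those rescued at the 6 h score.
- **Leave unrescued patients out.** The patients with the longest pain relief are removed, and the groups compared are no longer the randomised ones.

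At stake are the reported size of the effect on this outcome and the power of its test.

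**Working it through.** **Figures in the protocol.** It gives no rescue rate, event count or power for this outcome. Its only power statement concerns intra-operative narcotic use: difference 186.5 − 106 = 80.5 µg; SD √((21.6² + 16.4²)/2) = 19.18 µg; ratio 4.2. With 30 per group, power exceeds 99.9%, so the stated figure of more than 90% holds. It is not at issue here. Every rescue rate below is an assumption.

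**Step 1: what the mean reports.** Assume exponential times with median m, so the share unrescued at time t is S(t) = 2^(−t/m), with rescue recorded at the next of 0, 1, 2, 4, 6 h. With 6 h entered for the unrescued, the mean is 1 + S(1) + 2·S(2) + 2·S(4).

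- m = 6 h: 1 + 0.891 + 2(0.794) + 2(0.630) = 4.74 h; unrescued share S(6) = 0.50.
- m = 2 h: 1 + 0.707 + 2(0.500) + 2(0.250) = 3.21 h; unrescued share S(6) = 0.125.

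Among rescued patients only:

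- (4.74 − 6 × 0.50)/0.50 = 3.48 h
- (3.21 − 6 × 0.125)/0.875 = 2.81 h

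The difference is 4.74 − 3.21 = 1.5 h in one case and 3.48 − 2.81 = 0.7 h in the other. The means without any cut-off would be 6/0.693 = 8.7 h and 2/0.693 = 2.9 h. Neither reported mean estimates those.

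**Step 2: power.** Simulated with 30 per arm, two-sided 0.05, full follow-up to 6 h and times on the scoring grid. Log-rank uses the tie-corrected variance. MW is Mann-Whitney.

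| Assumed pattern | t, rescued only | t, 6 h entered | MW, 6 h entered | MW, unrescued last | Chi-square | Log-rank |
|---|---|---|---|---|---|---|
| (a) medians 6 vs 2 h | 22% | 86% | 86% | 91% | 91% | 94% |
| (b) 50% vs 90% rescued, same timing | 5% | 46% | 52% | 80% | 95% | 89% |
| (c) medians 3 vs 1 h | 63% | 95% | 93% | 94% | 88% | 98% |
| (d) medians 1.5 vs 0.5 h | 92% | 97% | 94% | 94% | 12% | 97% |

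In (d), 94% and 100% are rescued by 6 h, and apart from chi-square the choice hardly matters.

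**Step 3: an effect that wears off.** Patterns (a), (c) and (d) have proportional hazards, which favours log-rank. Under Study Procedures, Group A, the last caudal doses are at 0 and 1 h post-operatively, so an effect that fades within 6 h is plausible. Assume a control median of 2 h and a hazard ratio of 0.3 for the first 3 h, then as shown:

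| Hazard ratio after 3 h | t, 6 h entered | MW, 6 h entered | MW, unrescued last | Log-rank |
|---|---|---|---|---|
| 1 | 79% | 77% | 75% | 66% |
| 1.5 | 67% | 64% | 58% | 42% |
| 2 | 60% | 55% | 46% | 27% |

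Against correctly ranked Mann-Whitney, log-rank loses 75 − 66 = 9, 58 − 42 = 16 and 46 − 27 = 19 points.

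**Step 4: validity.** With no effect, full follow-up and equal medians of 3 or 6 h, type I error is 4.5% and 5.1% for Mann-Whitney with unrescued ranked last, and 4.8% and 5.4% for log-rank. With exits unrelated to pain in one arm only:

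- **20% vs 0% exiting:** 9–15% if the exit time is entered as a rescue time, about 6% if exits are ranked last, about 5% for log-rank.
- **10% vs 0% exiting:** 4–6% for all three.

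**The case against.** The strongest reply is that a valid test is already listed. Times heaped at 6 h are plainly non-normal, so the protocol's own rule points to Mann-Whitney. With unrescued patients ranked last and complete follow-up, that test holds its error rate and trails log-rank by only 3–4 points in (a), (c) and (d). This stands. A reader might infer that the listed tests are invalid or that log-rank is required. The document does not support that: log-rank loses to Mann-Whitney when the effect fades, and to the listed chi-square in (b).

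Second, the largest losses, 22% and 5% power, belong to a rescued-only analysis. A reader might infer that this is planned. The protocol does not say so; it only fails to exclude it.

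Third, the tie at 6 h may not arise. A patient reaching the pain threshold "at any point of time, will receive intravenous morphine 5mg", so rescue need not wait for a scheduled score. With continuous times, entering 6 h and ranking unrescued patients last give the same Mann-Whitney power: 91.5% in (a) and 78.9% in (b). This also stands.

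Fourth, patients are elective and ASA I–II, and early exit needs severe instability or re-operation. Marked imbalance in exits is therefore a remote prospect.

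Finally, handling of unrescued patients could be left to a statistical analysis plan, which is not shown. That does not remove the point. The protocol is not silent: it names a summary and a set of tests without qualification, and the mean, SD and t-test among them do not fit a censored time.

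**Conclusion.** The point holds for the summary and for the handling of unrescued patients. As stated, the mean, SD and t-test give this outcome no defined result, and the reported difference could halve or double with an unstated choice (0.7 or 1.5 h under the assumed medians of 6 and 2 h). It does not extend to a claim that one rank test is best. Log-rank gains a few points over correctly ranked Mann-Whitney under proportional hazards, and loses about 9 to 19 points in the fading-effect patterns tried.

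The size rests wholly on assumed rescue rates. It is moderate if many patients are unrescued at 6 h and small if nearly all are rescued. Only one secondary outcome is affected; the primary outcome and the sample size are not. This is a cheap improvement of minor severity.

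**What to change.** For time to first rescue only, replace the mean, SD and t-test as follows.

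- **Summary:** Kaplan-Meier curves by arm, with the median if reached, or a mean labelled as restricted to 6 h.
- **Patients and censoring:** include everyone with post-operative follow-up. Censor unrescued patients just after the 6 h score, or at earlier exit.
- **Test:** pre-specify one that uses all these patients, either log-rank (with a tie-corrected variance) or a Wilcoxon-type censored-data test (Gehan-Breslow). Mann-Whitney is acceptable if follow-up to 6 h is complete and unrescued patients are ranked after all rescued patients.
- **Reporting:** give the proportion rescued by 6 h and the early exits by arm, including patients who exit during surgery and so have no post-operative time.

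The cost is one or two sentences of text and one analysis that SPSS provides; no new data are needed. The choice of test is a trade-off to settle in advance: log-rank is weaker if the block's effect fades within 6 h, and weaker than chi-square if only the proportion rescued differs. None of these methods cures exits that are related to pain.

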2. AIM/ OBJECTIVES

The aim of this study is to evaluate the effectiveness of combined continuous caudal epidural with general anaesthesia versus general anaesthesia for intra operative and post operative analgesia in patients undergoing lumbar fixation, by recording intra operative and post operative analgesic requirements, blood pressure and heart rate and post operative patient-reported pain on the numeric pain scale score.

3. METHODOLOGY:

Patients and Methods

- **Type of the study:** Interventional, prospective, comparative randomized clinical trial.
- **Study Setting:** The operating theaters of Ain Shams University Hospitals.
- **Study period:** Over six months, after the approval of Medical Research Ethical Committee.
- **Study population:**

Inclusion criteria:

- Age group: Adult patients from age of 21 years to 60 years
- Sex: Both sexes.
- ASA Classification: patients with ASA classification I, II.
- Elective lumbar fixation surgeries.

Exclusion criteria:

- Patients refuse to give informed consent.
- Patients younger than 21 or older than 60.
- History of bupivacaine allergy.
- Emergency surgeries.
- Patients who underwent previous spine surgeries of any cause.

- Infection at the site of injection.
- Coagulopathy (acquired, induced, genetic).
- ASA Classification: ASA III, IV.
- Severe aortic stenosis, severe mitral stenosis, hypertrophic obstructive cardiomyopathy.
- Severe hypovolemia, Severe uncorrected anemia.
- Increased intra-cranial pressure (i.e., brain tumor or recent head injury).

Sampling method:

Patients will be randomly allocated by computer generated randomization into two equal groups A and B.

- **Group A:** Patients doing lumbar fixation with combined continuous caudal epidural and general anaesthesia.
- **Group B:** Patients doing lumbar fixation under general anaesthesia (opioid analgesia).

Sample size justification:

Using PASS 15 program for sample size calculation and according to (**Abdelhady et al., 2022**), the expected mean intra-operative narcotic consumption among study groups is $186.5 \pm 21.6 \mu\text{g}$ and $106 \pm 16.4 \mu\text{g}$.

Sample size of 30 patients per group can detect the difference between two groups with power $>90\%$ and alpha error 0.05.

Ethical considerations:

The study protocol will receive ethical approval from the Medical Research Ethical Committee, Faculty of Medicine, Ain Shams University. Informed written consent will be obtained from each patient before patients' allocation.

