
Study Procedures:

Patients will be randomly allocated into two equal groups.

Preoperative setting:

- Pre-operative assessment will be done by accurate history taking, full physical examination, laboratory and radiological investigations. including complete blood count (CBC), liver function test (LFT), kidney function test (KFT), prothrombin time (PT) and partial thromboplastin time (PTT) will be checked.
- All patient will be fasting for 8 hours pre operative.
- All patients will be informed about the study design, objectives and techniques.

- Informed consent will be signed by every patient prior to inclusion in the study.
- All patients will be educated about numeric pain scale score which 0 means no pain and 10 means worst imaginable pain.

Intraoperative setting:

- Standard perioperative monitoring will include pulse oximetry, electrocardiogram, end-tidal CO₂ measurement, inhaled volatile agent concentration and non-invasive blood pressure measurement.
- Baseline parameters such as oxygen saturation, systolic, diastolic and mean blood pressure, heart rate will be observed.
- Intravenous line will be inserted.
- For all patients, general anaesthesia will be induced by intravenous route using midazolam 0.04 mg/kg, fentanyl 1 µg/kg, propofol 2 mg/kg, atracurium 0.5 mg/kg.
- This will be followed by endotracheal intubation and mechanical ventilation. Maintenance of anaesthesia will be achieved by isoflurane 1.5% in oxygen and air (50:50) and atracurium 0.1 mg/kg every 20 minutes, so as to maintain end tidal CO₂ between 35 to 40 mm Hg.
- Intra operative heart rate and mean blood pressure will be recorded. Estimated blood loss will be determined.

Group A: (continuous caudal epidural with general anaesthesia “study group”)

- After induction of anaesthesia as mentioned above, patients will be located in the prone position for caudal epidural block. Sterile skin preparation and draping of the entire region will be completed in the standard fashion.

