- Fluoroscopy will be utilized and a lateral view will be obtained to demonstrate the anatomic boundaries of the sacral canal. With fluoroscopy, the caudal canal will appear as a translucent layer posterior to the sacral segments. The median sacral crest will be visualized as an opaque line posterior to the caudal canal. The sacral hiatus will be visualized as a translucent opening at the base of the caudal canal. The coccyx will be seen articulating with the inferior surface of the sacrum. A 17- or 18-gauge Tuohy-type needle will be inserted in the midline into the caudal canal. A feeling of a slight “snap” may be appreciated when the advancing needle pierces the sacrococcygeal ligament. Once the needle reaches the ventral wall of the sacral canal, it will be withdrawn and reoriented, directing it more cranially (by depressing the hub and advancing) for further insertion into the canal. The anteroposterior view will be used once the epidural needle is safely situated within the canal and the

epidural catheter will be advanced cephalad. In this projection, the intermediate sacral crests will appear as opaque vertical lines on either side of the midline. The sacral foramina will be visualized as translucent and nearly circular areas lateral to the intermediate sacral crests. Once the correct placement of the needle will be confirmed, a catheter will be inserted into the desired location while depth and position will be confirmed fluoroscopically.

- Before the local anaesthetic will be injected, careful aspiration or passive drainage is essential to exclude an unintentional intravascular or intrathecal needle location. An initial dose of 20 ml of 0.25% bupivacaine will be injected in the caudal canal in order to perform sensory block and spare motor power. Then a dose of 10 ml 0.25% bupivacaine will be injected through the epidural catheter every 1-hour intra operatively and at 0-hour and 1-hour post operative. Then the catheter will be removed 1 hour post operative.

Group B: (general anaesthesia “control group”)

- General anaesthesia will be induced as described above with administration of extra doses of fentanyl as needed according to hemodynamic changes suggesting pain sensation.

Post-operative setting:

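### Optional precision gain: adjust total intra-operative fentanyl for body weight, because a per-kg induction dose given before the block appears to count in the primary outcome

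*Protocol*

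**What the plan says.** - **Primary outcome** (Protocol, Measured outcomes): "Determining the total amount of fentanyl that will be consumed as intra operative analgesia". The list of assessed factors has the similar item "Total intra operative and post operative analgesia in both groups". Neither says whether the induction dose counts.
- **Induction** (Protocol, Intraoperative setting): "For all patients, general anaesthesia will be induced by intravenous route using midazolam 0.04 mg/kg, fentanyl 1 µg/kg". This applies to both groups.
- **Timing of the block** (Protocol, Group A): "After induction of anaesthesia as mentioned above, patients will be located in the prone position for caudal epidural block".
- **Further fentanyl** (Protocol, Group B): "administration of extra doses of fentanyl as needed according to hemodynamic changes suggesting pain sensation". No matching sentence appears for Group A.
- **Planning figures** (Protocol, Sample size justification): means of 186.5 µg (SD 21.6) and 106 µg (SD 16.4), 30 patients per group, alpha 0.05, power above 90%.
- **Analysis** (Protocol, Statistical analysis): Chi-square, "independent t-test or Mann-Whitney U-test according to the distribution of data". No covariate is named. The SAP, if there is one, is not at hand.

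**The concern.** If the induction dose counts, each patient's total has two parts. One is 1 µg per kg of body weight, fixed before the block. The other is whatever is given afterwards, and only that part can show a treatment effect. A two-group test on the total treats the weight-driven part as noise. A chance difference in mean weight between the groups also moves the estimated saving by 1 µg for every kg.

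At the planned effect, significance is close to certain. What the trial can usefully add is the size of the saving and how precisely it is known, and weight adjustment can sharpen that. Weight has to be known anyway for the per-kg drugs, so the gain is nearly free.

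**Working it through.** **Inputs.** From the Protocol: SDs 21.6 and 16.4 µg, difference 186.5 − 106 = 80.5 µg, 30 per group, induction dose 1 µg/kg. Assumed, because the Protocol gives no figure: weight SD 10-15 kg, and extra doses unrelated to weight. At 1 µg/kg, a weight SD of w kg contributes an SD of w µg.

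**1. The plan's own figure.** Pooled SD = √[(21.6² + 16.4²)/2] = √367.76 = 19.18 µg, so the standardised difference is 80.5/19.18 = 4.20. By the two-sided noncentral t, power is 96.3% at 3 per group and above 99.9% at 30. The stated power above 90% is reproduced.

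**2. Chance weight imbalance.** The SE of the difference in mean weight is w√(2/30): 2.58 kg at w = 10 and 3.87 kg at w = 15. Times 1.96, this is ±5.1 to ±7.6 kg, hence about ±5 to ±8 µg in the unadjusted difference. It is already part of the unadjusted SE and is not an extra error.

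**3. SE with and without adjustment.** Let S be the sum of the two group variances. The unadjusted SE is √(S/30). Adjustment removes 2w² from S and multiplies the SE by √(1 + 1/56) = 1.009 to allow for estimating the slope. From the planning SDs, 21.6² + 16.4² = 735.52.

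| Setting | w (kg) | Unadjusted SE (µg) | Adjusted SE (µg) | Change |
|---|---|---|---|---|
| Weight variance on top of planning SDs | 10 | √(935.52/30) = 5.58 | 1.009·√(735.52/30) = 5.00 | −10.5% |
| Same | 15 | √(1185.52/30) = 6.29 | 5.00 | −20.5% |
| Weight variance within planning SDs | 10 | √(735.52/30) = 4.95 | 1.009·√(535.52/30) = 4.26 | −13.9% |
| Same | 15 | 4.95 | 1.009·√(285.52/30) = 3.11 | −37.1% |
| Extra doses in 50 µg steps, Poisson means 0.5 and 2 (SDs 35 and 71 µg) | 10 | √(6450/30) = 14.66 | 1.009·√(6250/30) = 14.56 | −0.7% |
| Same | 15 | √(6700/30) = 14.94 | 14.56 | −2.6% |
| Total unrelated to weight | any | 4.95 | 5.00 | +0.9% |

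**4. Check by simulation** (40,000 trials per setting; Welch interval against a linear model on group and weight with HC3). The SE fell by 10.6% and 20.8% (on top), 13.5% and 37.5% (within), and 0.7% and 2.7% (50 µg steps). It rose by 0.8% with no weight effect. Bias was within 0.03 µg in the first two settings, and HC3 coverage there lay within 94.7-95.7%.

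**5. What this does to the interval.** The 95% half-width falls from 11.1-12.5 to 10.2 µg (on top) and from 9.9 to 8.7-6.4 µg (within). With no weight effect it goes from 9.9 to 10.2 µg. HC3 is slightly conservative at this sample size, so the interval gains a little less than the SE does.

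**6. Does the induction dose count?** Extra fentanyl is described only for Group B. If induction were excluded, Group A's total as written would be zero, against a lower planning mean of 106 µg. If induction were included and nothing more given, 106 µg at 1 µg/kg would need a mean weight of 106 kg. Inclusion is the more natural reading, but neither squares easily with the planning mean.

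**The case against.** The case against is strong on four counts.

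- **The planned tests are valid.** Both are legitimate for a randomised comparison. The analysis section is one generic sentence for all outcomes, and a SAP that is not at hand could add a covariate. This stands, and it is why the point is an improvement and not an error.
- **No conclusion would change at the planned effect.** With a difference of 80.5 µg and weight variance within the planning SDs, the lower 95% limit moves from 80.5 − 9.9 = 70.6 µg to between 71.8 and 74.1 µg. The plan does not name a confidence interval either. This also stands; the gain is in precision only.
- **The size of the gain rests on assumptions.** No weight SD is given. The upper end is strained: at 15 kg within the planning SDs, the SD of 16.4 µg leaves only √(16.4² − 15²) = 6.6 µg for everything other than weight. A reader might infer a gain of about 41% by supposing that Group A receives induction fentanyl only. The documents do not support that, since it conflicts with the 106 µg planning mean.
- **The premise is conditional.** The outcome wording refers to analgesia, so the induction dose could be held not to count, and the weight issue would then vanish. The 106 µg comes from a cited discectomy study whose fentanyl regimen cannot be seen here, so it is only indirect evidence for inclusion. The definition therefore needs to be stated.

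In addition, the simulations compare with the Welch t interval only. No gain over Mann-Whitney has been shown, so that test need not be dropped.

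**Conclusion.** The point holds as an optional, nearly free improvement. If the induction dose counts, the unadjusted comparison leaves weight-driven variation in the error. Adjusting for weight would reduce the SE of the fentanyl saving by about 11-38% if the planning SDs hold, by 1-3% if extra doses vary far more, and would raise it by about 1% if the total is unrelated to weight. These figures assume a weight SD of 10-15 kg and extra doses unrelated to weight.

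Three stronger readings are not supported. The planned test is not biased. The trial is not underpowered for 80.5 µg. The statement of power above 90% is true as written and needs no correction.

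One matter rests on the text alone: the description of extra fentanyl for Group B only does not fit easily with the planning means, and the two passages must be reconciled.

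**What to change.** - **Statistical analysis:** pre-specify, as the primary estimate, a linear model of total intra-operative fentanyl (µg) on group and body weight with robust (HC3) standard errors, and report the group difference with its 95% confidence interval. Robust errors suit the unequal planning SDs. The Mann-Whitney test may stay as a sensitivity analysis.
- **Measured outcomes:** state that the total includes the induction dose, and report fentanyl given after induction separately.
- **Group A and Group B procedures, and Sample size justification:** reconcile the description of extra fentanyl for Group B only with the two planning means. Which arrangement applies is for the investigators to state.

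The cost is a few sentences, one degree of freedom (57 instead of 58) and recording body weight, which the per-kg doses already require. No patient or procedure changes. The choice should be fixed before outcome data are seen, so that the covariate is not picked afterwards.
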